1.0 Objectives / Specific Aims

Normal aging is characterized by changes in the immune system that result in increased susceptibility to infections, poor response to new vaccine antigens, loss of protection offered by previous vaccinations and decreased immune surveillance [1, 2]. Despite the chronic inflammation associated with immunosenescence, the aging population is living longer. Consequently, individuals >65 years of age, are the most rapidly growing population amongst those with end stage renal disease (ESRD) and account for more than 18% of renal transplant (RT) recipients [3].

The incidence of pneumococcal disease is significantly higher in both elderly [4] and those with RT [5] and the combination of these factors is likely additive, if not synergistic, for invasive pneumococcal disease (IPD). It is recommended that both elderly >65 and RT recipients be vaccinated with a regimen that includes both the 13-valent pneumococcal conjugate vaccine (PCV13) and the 23-valent pneumococcal polysaccharide vaccine (PPV23). However, small immunogenicity studies performed in the transplant populations have not shown superiority of a PCV containing regimen [6, 7]. Moreover, the addition of PCV to the pneumococcal vaccine regimen does not improve protective immunity in this population. Studies to date fail to elucidate the possible foundation of the disappointing immune responses to the PCV regimens, data essential for the development of a rational and effective next generation pneumococcal vaccine.

Specific Aim 1.

We will **define immune responses by measuring** serum antibody and functional antibody responses to PPS 14, 19A and 23F following PCV13 vaccination in RT recipients 65-75 years of age and compare these to: RT recipients 35-45 years of age and persons with DM/HTN but normal function 65-75 years of age to dissect out the age and RT components respectively. Healthy persons 35-45 and 65-75 years of age will be studied as age appropriate reference.

Specific Aim 2.

We will measure and characterize the antigen-specific B cell subset response following immunization with PCV13 in the RT recipients 65-75 years of age and compare them to each of the groups described in Specific Aim 1 using flow cytometry and fluorescently labeled PPS and monoclonal antibodies. These measures will be correlated with post-immunization functional antibody activity, a surrogate of protection.

Specific Aim 3.

We will measure TNFR expression by B cells following immunization with PCV13 in 65-75 year old RT and compare them to each of the groups described in Specific Aim 1. Gene expression, with focus on the B cell activating factor (BAFF) system, will be measured in PPS-specific and non-PPS specific B cells using single cell genomics and flow cytometry. These measures will be correlated with post-immunization functional antibody activity, a surrogate of protection.

Our central hypothesis is that the aging RT population responds poorly to PCV13 vaccination reflecting the combined effects of aging and RT. We postulate that both the number of memory B cells and expression of tumor necrosis factor (TNF) superfamily receptors, which play crucial roles in the response to pneumococcal polysaccharides (PPS), are deficient in the elderly RT population and contribute to poor pneumococcal vaccine responses.

We have developed fluorescently labeled PPS allowing us to study the nature and surface receptors of PPS-specific B cells. Our preliminary data demonstrate that RT recipients 1. Respond poorly to pneumococcal immunization as measured by antibody titer and functional antibody activity. 2. RT recipients and healthy elderly have lower absolute number of both IgM and switched memory B cells. 3. The number of PPS-specific IgM and switched memory B cells are significantly lower in RT recipients and 4. TACI and BAFF-R, members of the TNF superfamily receptors, expression is significantly lower in the PPS-specific memory B cells in the RT population versus healthy controls. The overall objective of this proposal is to characterize the immune response and explore possible mechanisms of poor vaccine responsiveness following immunization with PCV in the rapidly growing group of elderly with RT. As the RT population is a

heterogeneous group we will study only those in whom the underlying cause of renal failure is diabetes mellitus type 2 (DM2) and/or hypertension (HTN).

2.0 Background

Streptococcus pneumoniae is the most common bacteria isolated from the elderly with community acquired pneumonia [8]. The elderly are at high risk of pneumococcal infection, have an increased incidence of blood stream infection and a higher mortality rate compared to younger adults [4]. It is projected that between 2000 and 2040, the number of Americans ≥ 65 years of age will more than double. The rapid growth of the aging population has resulted in a significant increase in elderly individuals with end-stage renal disease (ESRD). In 2014, there were $>300,000$ older adults with ESRD, a seven-fold increase compared to the 1990's [3]. In addition, individuals with ESRD are living longer, disproportionately increasing the number of elderly with ESRD [9]. Moreover, older (>65 yrs) individuals now account for 18.4% of the 17,000 renal transplants performed in the US annually [3, 10] and are by far the fastest growing population requiring renal replacement therapy, i.e. dialysis or renal transplantation [11]. Although the renal transplant (RT) population is susceptible to a host of infections, *S. pneumoniae* is the most common bacterial respiratory pathogen and the incidence of invasive pneumococcal disease (IPD) is estimated to be 12.8 fold higher than in the general population [5]. Moreover, aging individuals with RT have two distinct risk factors for pneumococcal disease, namely age and RT accounting for the high incidence of disease in this population.

Accordingly, pneumococcal vaccination is recommended for all adults ≥ 65 years of age and all RT recipients [12, 13]. In 2012 the vaccination recommendations by the Advisory Committee on Immunization Practices (ACIP) for these immune compromised adults, were changed to include vaccination with the 13-valent pneumococcal conjugate vaccine (PCV13) [12]. Although highly successful in infants, immunogenicity studies have overall failed to demonstrate superiority of PCV based regimens in older adults [14]. Similarly, a prime-boost regimen based on sequential immunization with PCV7 and the 23-valent pneumococcal polysaccharide vaccine, Pneumovax[®] (PPV23), has not demonstrated improved responses in RT and liver transplant populations [6, 7]. The RT population ≥ 65 years of age is rapidly growing and represents a unique subpopulation with combined immunodeficiencies related to aging [15] and immunosuppressive drugs related to transplant. Both aging and RT result in a marked increased risk of pneumococcal disease with decreased immune response to pneumococcal vaccination. The immune response to vaccination with PCV is poorly characterized in the aging and transplant populations, and may not be more effective than PPV23 alone, implying the need for alternate vaccine/adjuvant strategies. Moreover, studies characterizing and comparing antigen-specific B cell responses in well-defined RT populations are lacking.

We have developed directly labeled fluorescent PPS to enumerate and characterize PPS-specific B cells. This allowed the analysis of antigen-specific B cell responses to pneumococcal vaccination. The results of these studies demonstrated that the immune response to PPV in young adults consists predominantly of IgM memory B cells [16]. In contrast, in the elderly who are deficient in memory B cells, particularly IgM memory B cells [17], the predominant B cell phenotype in response to PPS consists of switched memory B cells (IgG/A+IgM-CD27+)[18]. HIV+ individuals, are also deficient in CD27+IgM+ B cells yet the predominant response consists of PPS-specific CD27+IgM+ B cells [19-22], albeit at significantly reduced numbers. Thus, the cause of poor pneumococcal vaccine responses varies according to study population. Several investigators and our preliminary data show that like the elderly and HIV-positive, absolute number and percentage of memory B cells are significantly lower in stable RT recipients, at 6 months to 5 years post-RT, compared to healthy subjects [23, 24]. Moreover, low number and percentage of IgM memory B cells correlate with poor antibody responses to PPV23.

This may however not be the only cause for poor vaccine responses. The ability to isolate antigen-specific B cells allows us to explore other deficits and/or changes in surface markers and gene expression potentially implicated in poor vaccine responses. It has been well described that members of the TNFR family and

certain Toll like receptors (TLR) play a crucial role in the immune response to pneumococcal vaccination [25, 26]. As shown in preliminary data, we have found decreased TACI and BAFFR expression in PPS-specific B cells derived from RT recipients. Although the number of RT recipients studied is very small, it was a consistent finding and merits further study. Adjuvants that specifically upregulate TACI expression, such as CpG-ODN, could therefore effectively increase immune responsiveness to pneumococcal vaccines. This strategy has shown to increase immune and memory responses to the conjugate pneumococcal vaccine in HIV-positive persons [27]. Our central hypothesis is that the elderly RT population responds poorly to PCV13 reflecting combined effects of aging and RT that result in abnormalities in both number of memory B cells and TNF superfamily expression, which play crucial roles in the response to polysaccharide antigens. We will test this hypothesis by measuring PPS-specific antibody and opsonophagocytic antibody responses, PPS-specific B cell phenotypes and surface and gene expression of the TNFR with known role in response to pneumococcal vaccination and correlate these individually with antibody and functional antibody responses. This has important clinical implications as deficient TNFR expression can be modulated by the addition of adjuvants such as CpG-ODN.

Preliminary Data

Over the past 16 years, the PI's laboratory has studied the immune response to pneumococcal vaccination. All of these studies have been performed in humans. Initially these studies were focused on the elderly population. We defined immune response, functional antibody activity and antibody (V) gene usage in this population. We have developed unique directly labeled fluorescent pneumococcal polysaccharides (PPS). This has allowed us to focus on the antigen-specific B cell response. The PPS-specific immune response, including antibody response, functional activity and B cell phenotype analysis have been performed by us following pneumococcal polysaccharide vaccination (PPV23) and/or pneumococcal conjugate vaccine (PCV13), in young and elderly (>65 yrs) healthy persons as well as young (<50) and aging (50-65 yrs) HIV+ persons. These studies were published in Journal of Immunology, Journal of Infectious Diseases, Vaccine, PlosOne and the Journal of AIDS and Clinical Research . These studies have formed the basis for comparative analysis of the immune response following PCV13/PPV23 in elderly and HIV+ individuals. The results of these studies demonstrated unique B cell deficiencies in HIV and elderly. We are in a unique position to perform an in-depth analysis of the immune response to PCV13 in the aging renal transplant population, defining surrogates of efficacy and safety. Despite the recent change in vaccine recommendation, based on expert opinion, studies demonstrating superiority and safety of PCV has not been performed in an adequate manner in the past. In addition, we will explore the mechanism of poor responses, laying a foundation for development of more effective vaccines for this population of elderly.

3.0 Intervention to be studied (if applicable)

The intervention to be studied is the immune response to immunization with PCV13 or Prevnar®13. This FDA approved vaccine is given as part of the standard of care in Groups 1-4. The experimental part of the protocol in these groups will be blood draws at days 0, 7, 30 and years 1 and 2 in these groups.

In Group 5 two interventions will occur: 1. Immunization with the FDA approved PPV23 or Pneumovax® 23 and 2. PCV13 a FDA approved vaccine. In addition, blood samples will be obtained at days 0, 7, 30 year 1 and year2.

Both PPV23 and PCV13 are FDA approved vaccines for use in humans. PCV13 is recommended for all individuals enrolled in Groups 1-4. It is not recommended as routine part of care in Group 5 enrolled individuals however it has never shown to be harmful in this group of individuals.

4.0 Study Endpoints (if applicable)

The primary endpoint of this study is: quantify the antibody titers in mg/mL and opsonophagocytic antibody titer calculated as serum dilution, number of polysaccharide specific B cells, and absolute number of cells/mL induced by vaccination with PCV13.

Secondary endpoint of the study is to describe differences in gene expression of 56 genes to be determined by single cell PCR and comparing these between groups.

The primary safety endpoint of the study is measured as minimal versus moderate local side effect. Minimal side effect measured as no impairment in activity. Moderate local side effect is a side effect affecting use of the extremity for less than 24 hours.

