3. Known anaphylaxis, hypersensitivity or “bad allergic reaction” to the pneumonia vaccine. This does not include egg allergy or previous Guillan Barre syndrome.
4. Those who received blood products or gamma globulin within 3 months.
5. Inability to comprehend or sign the informed consent form
7. Previous/present illness that may affect immune response to the vaccine (previous pneumococcal Disease, removal of the spleen, auto-immune disease such as lupus or rheumatoid arthritis, end-stage liver disease, or cancer)
8. Significant abnormalities (3xULN and all those considered to be critical values) in CBC, chemistries including glucose.
9. HIV, HBsAg or HCV positivity
10. Receipt of PPV23 within 1 year

Groups 1 (65-75 yrs) and 2 (35-45 yrs) Renal Transplant populations

Inclusion Criteria:

Age range; RT 35-45 or 65-75 years old,
 End stage renal disease cause either DM2 and/or hypertension (HTN)
 Renal transplant >12 months ago
 We will not restrict volunteers with respect to gender, ethnic or racial group.

Exclusion criteria:

1. Medications that are known to affect immune function (chemotherapy, anti-TNF α agents) with the exception of anti-rejection medication.
 2. Episode of acute rejection within the last 6 month period
- The inclusion/exclusion criteria will be determined by chart review and pregnancy test for females of child bearing potential.

Group 3: Diabetic/hypertensive 65-75 year old controls

Inclusion Criteria

65-75 years old with DM2 and/or HTN.
 Previous immunization with PPV23 >1 year prior
 Willingness to be tested for HIV, HBV and HCV
 “normal kidney function” defined as glomerular filtration rate (GFR) of 60% or above
 We will not restrict volunteers with respect to gender, ethnic, or racial group.

Exclusion Criteria

1. Medications that are known to affect immune function (chemotherapy, anti-TNF α agents).

The inclusion/exclusion criteria will be determined by chart review.

Group 4: Healthy Control 65-75 yr old

Inclusion Criteria

65-75 years old without DM2. May have high blood pressure (systolic>140 and/or diastolic>90) as long as it is well controlled (systolic<140 and/or diastolic <90) and has not affected kidney function.
 Previous receipt of PPV23 > 1 year prior
 Willingness to be tested for HIV, HBV and HCV
 We will not restrict volunteers with respect to gender, ethnic, or racial group.

Exclusion Criteria

6. Medications that are known to affect immune function (chemotherapy, anti-TNF α agents).

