Vaccination with the pneumococcal vaccine is linked with side effects that are usually considered minor side effects. In adults aged 18 years and older, the most commonly reported solicited adverse reactions (>5%) PCV13, or Prevnar were pain at the injection site (>50%), fatigue (>30%), headache (>20%), muscle pain (>20%), joint pain (>10%), decreased appetite (>10%), injection site redness (>10%), injection site swelling (>10%), limitation of arm movement (>10%), vomiting (>5%), fever (>5%), chills (>5%), and rash (>5%). The most common adverse reactions, reported in >10% of subjects vaccinated with PPV 23 or Pneumovax in clinical trials, were: injection-site pain/soreness/tenderness (60.0%), injection-site swelling/induration (20.3%), headache (17.6%), injection-site erythema (16.4%), asthenia and fatigue (13.2%), and myalgia (11.9%). Sometimes an allergic reaction can occur but this is very rare. The side effects are seldom more severe and may consist of fever, redness at the site of injection with lymph node swelling in the armpit which may last up to 3 days. This occurs rarely. It should be noted that pneumococcal vaccination (PCV13) is recommended for all RT recipients and all individuals >65 years of age where it is considered standard of care. All individuals in groups 1-4 will already have received PPV23 as part of their routine health care. Although both PPV23 and PCV13 vaccines are FDA approved, two vaccine regimen is not routine as standard of care in healthy HIV negative persons <65 although it is safe, so this vaccination is experimental in this use. Thus as healthy young control group, 35-45 years of age, an essential part in this study for comparator reasons, we will immunize with PPV23 a year before immunizing them with PCV13 so that all groups have received both PPV23 followed by PCV13. Again, a step absolutely necessary and safe, to generate interpretable data from this study.

All paperwork containing donor identifiable data is held in a locked file cabinet in the office of the PI. Each donor is assigned a random number and all samples resulting from that donor (blood, serum, cDNA) are labeled with that number. No donor identifiable data is used to mark samples. All staff who have completed appropriate IRB and HIPAA training and are aware of the importance of maintaining donor confidentiality.

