The risk of pneumococcal vaccination adverse side effects is minimal. In the rare event that an adverse reaction of greater magnitude than local reaction occurs, each volunteer is provided with a contact telephone number to reach research personnel who will see and potentially treat the adverse reaction as appropriate. The most common of these occasional adverse reactions consists of low grade fever, malaise and swollen lymph nodes, treatable with 2 days of prednisone. Adverse events associated with blood draws are rare and most commonly consist of prolonged bleeding treated with the application of local pressure.

All adverse events will be monitored and recorded. Monitoring will take place at every visit by the study coordinator and the P.I.

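### The primary safety endpoint has only two categories, both local, so systemic reactions and local effects of 24 hours or more fall outside it, and no safety summary by group is planned for them.

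*Combined protocol and SAP*

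**What the plan says.** Section 4.0 defines the endpoint: "The primary safety endpoint of the study is measured as minimal versus moderate local side effect". The lower grade means that activity is not impaired. The upper grade is defined thus: "Moderate local side effect is a side effect affecting use of the extremity for less than 24 hours". There is no third grade and no systemic category.

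Section 15.0 lists the common PCV13 reactions in adults of 18 and over. Among them are "fatigue (>30%), headache (>20%), muscle pain (>20"%), and further down the list vomiting, fever, chills and rash, each above 5%. Later the same section refers to stronger reactions: "In the rare event that an adverse reaction of greater magnitude than local reaction occurs". It gives examples: "The most common of these occasional adverse reactions consists of low grade fever, malaise and swollen lymph nodes".

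Section 13.0 has every adverse event recorded on an event form at each visit, characterised by severity, relatedness and outcome among other things, and reviewed quarterly by a safety committee. It also states a safety endpoint of its own, covering the vaccination and the blood draws in general, without a measure. Section 12.0, which holds the statistical plan, contains no safety analysis. The list of data items in section 10.0 has no adverse event entry, although Tables 1 to 3 there schedule side-effect reports at the visits after vaccination.

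**The concern.** An endpoint should be able to register the events that the plan itself expects. This one grades arm function only. A participant with fever and vomiting but a usable arm has no systemic category to enter, and one whose arm is impaired for two days exceeds the top grade.

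The background in section 2.0 describes earlier safety work on conjugate vaccine as inadequate and speaks of "defining surrogates of efficacy and safety" in older transplant recipients. If section 4.0 is followed literally, the headline safety statement for those recipients would be silent on systemic reactions and on longer local ones. The information would exist on event forms, but nothing in the plan says how it is to be summarised, so what is reported would be decided after the data are seen.

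**Working it through.** The plan gives no sample size, power, significance level or threshold for safety, so there is no stated figure to reproduce. The check has two parts: what the endpoint can classify, and how many expected events it leaves out.

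**1. What the endpoint can classify**

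| Event | Category in section 4.0 |
|---|---|
| Local effect, activity not impaired | minimal |
| Local effect, use of limb impaired for under 24 hours | moderate |
| Local effect, use of limb impaired for 24 hours or more | none |
| Any systemic reaction | none |

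The PCV13 list in section 15.0 has 13 entries. Four are local: injection-site pain, redness, swelling, and limited arm movement. The other nine are systemic on a plain reading: fatigue, headache, muscle pain, joint pain, decreased appetite, vomiting, fever, chills and rash. The split is mine, since the document does not label them.

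**2. Expected numbers outside the endpoint**

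Inputs:
- Group size: 40 from section 12.0 (200 in five groups), or 55 from section 6.0 (275 / 5, assuming equal groups).
- Rates: the lower bounds in section 15.0. They describe adults in general, and applying them to each study group is an assumption.

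Expected number = group size × rate.

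| Reaction | Rate (lower bound) | n = 40 | n = 55 |
|---|---|---|---|
| Fatigue | 0.30 | 12 | 16.5 |
| Headache | 0.20 | 8 | 11 |
| Muscle pain | 0.20 | 8 | 11 |
| Joint pain | 0.10 | 4 | 5.5 |
| Fever | 0.05 | 2 | 2.75 |

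The rows must not be added together, because one participant can have several reactions.

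Probability of at least one fever in a group, 1 − (1 − 0.05)^n:
- n = 40: 1 − 0.95^40 = 0.87
- n = 55: 1 − 0.95^55 = 0.94

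So each group will probably contain at least one reaction of a kind that section 15.0 places above a local one, and the endpoint cannot show it. These rates also sit badly with the same section's statement that greater-than-local reactions are rare.

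**3. What a descriptive table would deliver**

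Exact (Clopper-Pearson) two-sided 95% intervals for x events in n have lower limit Beta(0.025; x, n − x + 1) and upper limit Beta(0.975; x + 1, n − x).
- Fatigue, 12 of 40 (30%): 16.6% to 46.5%
- Fever, 2 of 40 (5%): 0.6% to 16.9%

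These intervals are wide. They suit a description by group, not a test between groups.

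**4. The two safety endpoint statements**

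Section 4.0 is specific but local only. Section 13.0 is broad enough to take in systemic events, but names no measure, time point or summary. Neither section refers to the other.

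**The case against.** The strongest reply is that nothing is lost. Sections 13.0 and 15.0 have all adverse events monitored and recorded, a committee reviews them quarterly, and section 13.0 words the safety endpoint broadly enough to include fever or vomiting. PCV13 is standard of care in Groups 1 to 4, no specific aim concerns safety, and section 15.0 describes the side effects as usually minor. All of this stands, and it limits the point to the definition of the primary safety endpoint and the missing summary. It does not remove the point: recording an event does not say how it will be reported, and two sections that define the safety endpoint differently need reconciling in any case.

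A reader might infer four stronger things, which the documents do not support:

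- **That systemic reactions are kept out of the safety results altogether.** They are kept out of the primary safety endpoint only. General adverse event recording captures them.
- **That the plan ranks all nine systemic reactions above local ones.** Section 15.0 names low grade fever, malaise and swollen nodes, and of these only fever appears by name in the PCV13 list.
- **That the plan promises a safety comparison across the five groups.** Section 2.0 speaks of surrogates of efficacy and safety, and no between-group safety test is specified anywhere.
- **That transplant rejection should be in the endpoint.** Rejection as an event appears only in an exclusion criterion, "Episode of acute rejection within the last 6 month period", for which no reason is given. The documents never name rejection as a vaccine risk, and there is no unvaccinated transplant arm against which to attribute it. Chart follow-up at yearly visits would also be new data collection.

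**Conclusion.** The point holds in a limited form. As defined in section 4.0, the primary safety endpoint cannot register systemic reactions or local effects of 24 hours or more. At the plan's own lower-bound rates this leaves out at least 12 (16.5) participants' fatigue and 2 (2.75) participants' fever in a group of 40 (55). The figures assume that general adult rates carry over to each study group, including transplant recipients, and for 55 that the groups are equal in size.

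The events are recorded, so this is a gap in endpoint definition and planned reporting and not a failure of safety monitoring. It does not affect the immunology aims. Rejection is not part of the conclusion; any reported episode would appear in the adverse event listing. The change is a cheap improvement worth making.

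**What to change.** 1. **Section 4.0:** define the primary safety endpoint as each participant's worst reaction after PCV13, local or systemic, graded by effect on activity, with a category for effects lasting 24 hours or more. Use the reaction list in section 15.0 as the checklist.
2. **Section 13.0:** refer to that definition, so that the plan has one safety endpoint. Keep the general adverse event recording as it is.
3. **Section 12.0:** add a descriptive table by group, with local and systemic components shown separately and exact 95% confidence intervals, and no hypothesis test. State the denominator, for example all who received PCV13 and gave at least one side-effect report.
4. **Time window:** state one window for all groups. The first visit after vaccination may fall on day 5, 7 or 10 in the transplant groups and is on day 7 elsewhere. The day 30 visit (day 396 in Group 5) is common to all.
5. **Section 10.0:** add the reaction grades to the list of data items.

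The cost is a tick-list on the existing event form and one extra descriptive table. Side-effect reports are already scheduled in Tables 1 to 3, so no visits or samples are added.

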Statistical Analysis Plan and Sample Size Justification for Aim 3

Aim 3 will examine differences in expression of TNFR markers (TACI, BCMA, and BAFF-R) using single cell qPCR on a subset of 10 participants (5 responders and 5 non-responders) from each of the 5 groups described in Aims 1 and 2 evaluated at baseline and 7 days post-vaccination. Single cell qPCR allows us to not only evaluate differences in expression between groups but also allows us to estimate the within subject and within group heterogeneity with great precision. Each participant sample provides between 40-96 viable cells that will be evaluated for gene expression at the single cell level. Relative fold-change in expression between participants who are 65-75 RT, 35-45 RT, or 65-75 DM/HTN with respect to the relevant controls will be evaluated using a linear mixed model approach. The model will include fixed effects for participant group, response status, and time and a random subject effect to account for repeated measurements resulting from individual cells from the same subject samples. Comparisons of number of gene expression between groups and within group between times will be evaluated using a series of contrasts from the LMM. For comparisons within group between responders and non-responders, a sample size of 5 responders and 5 non-responders with ≥ 40 cell level measures at 2 time points provides 80% power to detect 2.7 fold-increase or a 0.60 fold-decrease in expression using a two-sided test assuming within subject correlation of 0.5 and a Bonferroni corrected significance level (up to 10 comparisons) of $p = 0.005$. For comparisons between groups, we will have 10 subjects per group allowing us to detect even smaller fold-changes in expression.

All electronic data will be kept on the VA secure V drive or R drive and on MUSC secure Z drive that only team members will have access to.

13.0 Provisions to Monitor the Data to Ensure the Safety of Subjects (if applicable)

All adverse events (AE) will be reported and monitored through the data safety monitoring plan. The AE's will be characterized by: intensity/severity; expectedness; relatedness; frequency; outcome; treatment or action taken.

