Monitoring will be performed at each study visit by the study coordinator and/or P.I. and will occur at the Ralph H. Johnson VA Medical Center and MUSC and all AEs will be recorded on an event form with physician/nurses/coordinator notes attached. These will be reviewed by the safety monitoring committee. The safety monitoring committee will include board certified Infectious Diseases specialists. Meetings will occur on a quarterly basis. [name], the P.I. will arrange for the meetings quarterly, make all materials available for review by the committee and be ultimately responsible for the meetings.

The study endpoints will be reporting and assessing safety of the vaccination and blood draw procedures and to ensure that these procedures are well within the acceptable complication risk associated with vaccination and blood draws.

All serious, unexpected, AND related adverse events will be reported to the MUSC IRB within 10 working days of learning of the event.

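### The primary safety endpoint is not exhaustive: a local reaction that impairs the limb for 24 hours or more fits neither of its two levels

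*Combined protocol and SAP*

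**What the plan says.** Section 4.0 (Study Endpoints) states: "The primary safety endpoint of the study is measured as minimal versus moderate local side effect". It then defines the two levels. For the lower: "Minimal side effect measured as no impairment in activity". For the upper: "Moderate local side effect is a side effect affecting use of the extremity for less than 24 hours". No third level follows.

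Section 13.0 (safety monitoring) covers adverse events in general: "The AE's will be characterized by: intensity/severity; expectedness; relatedness; frequency; outcome; treatment or action taken". It adds that "all AEs will be recorded on an event form with physician/nurses/coordinator notes attached", with quarterly review by a safety monitoring committee. It gives no severity scale and no duration cut-off, and it does not refer back to the two levels in section 4.0. The visit tables in section 10.0 schedule the reporting of side effects at follow-up visits.

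Section 15.0 (Risks to Subjects) lists limitation of arm movement in more than 10% of adults after PCV13, with no duration. It separately describes more severe reactions, said to be rare, that include fever and "redness at the site of injection with lymph node swelling in the armpit which may last up to 3 days".

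The statistical analysis text in section 12.0 covers Aims 1 to 3 and contains no safety analysis.

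**The concern.** A categorical endpoint should have a place for every participant, above all at its worst end. Here the top level has an upper limit on duration and nothing above it, so the reactions left without a level are the longest-lasting ones. The risk section expects limited arm movement to be fairly common, and nothing in the documents says that it always resolves within a day.

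What is at stake is how the named primary safety result is classified and reported. Faced with a two-day impairment, one member of staff may leave the endpoint field blank and another may enter moderate. The tabulated result would then depend on who filled in the form. The background section says that earlier work has not adequately shown the safety of the conjugate vaccine, and both vaccines are part of the experimental protocol in Group 5. The safety summary should therefore be well defined.

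**Working it through.** The documents give no rate, test or sample size for the safety endpoint, so there is no planned figure to reproduce. The check has two parts.

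**1. Are the levels exhaustive?** Each possible local outcome is set against the section 4.0 definitions.

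| Outcome | Minimal (no impairment in activity) | Moderate (use of extremity affected, under 24 h) |
|---|---|---|
| No local reaction | Only if folded in; not stated | No |
| Reaction, no impairment | Yes | No |
| Use of extremity affected, under 24 h | No | Yes |
| Use of extremity affected, 24 h or more | No | No |
| Activity impaired, use of extremity not affected | No | No |

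The fourth row is the main gap. The first and last rows are smaller gaps of the same kind. Sections 10.0, 13.0 and 15.0 were read for a further level or a rule mapping adverse events to the endpoint. None was found. Duration is not among the adverse event characteristics listed in section 13.0.

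**2. How many participants might be affected?** This is for scale only.

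Inputs:
- Rate of limited arm movement after PCV13: more than 10% (section 15.0). The lower bound, 0.10, is used and applied to all groups alike.
- Number of participants: 275 (section 6.0), or 200, which is 40 per group (sample size text, section 12.0).
- Share *f* of those limitations lasting 24 hours or more: not in the documents. Assumed to be 10%, 25% or 50%.

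Formulas: participants with limited arm movement = N × 0.10. Participants without a level = N × 0.10 × *f*. Chance of at least one = 1 − (1 − 0.10*f*)^N.

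Limited arm movement: 200 × 0.10 = 20; 275 × 0.10 = 27.5.

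| *f* (assumed) | Without a level, N = 200 | Without a level, N = 275 |
|---|---|---|
| 10% | 20 × 0.10 = 2 | 27.5 × 0.10 = 2.75 |
| 25% | 20 × 0.25 = 5 | 27.5 × 0.25 = 6.9 |
| 50% | 20 × 0.50 = 10 | 27.5 × 0.50 = 13.75 |

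The range is therefore 2 to 10 of 200, or about 3 to 14 of 275. The two sample sizes should be kept apart. At *f* = 10% the chance of at least one such participant is 1 − 0.99^200 = 0.87 for 200 and 1 − 0.99^275 = 0.94 for 275. If *f* is close to zero, so is the count.

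**The case against.** The strongest reply is that this is a labelling gap and not a loss of safety data. Section 13.0 requires all adverse events to be reported, characterized for severity, entered on a form with notes and reviewed by a committee. It even describes the assessment of vaccination safety as a study endpoint. No test, threshold or stopping rule depends on the split between minimal and moderate. In Groups 1 to 4 PCV13 is standard of care, not part of the experimental protocol. All of this stands, and it limits the consequence. It does not close the gap, because section 13.0 has no scale, no duration field and no link to the section 4.0 levels.

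The documents do not support three stronger readings that a reader might infer:

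- **That the safety summary will look better than the data.** Nothing says that longer reactions would be dropped or downgraded. The definition leaves their handling open, and the adverse event record could still show them.
- **That the protocol itself expects limb impairment beyond 24 hours.** The text "lymph node swelling in the armpit which may last up to 3 days" belongs to a description of fever, redness and node swelling, said to occur rarely. It does not mention use of the limb. The figure for limited arm movement carries no duration.
- **That the counts above are a forecast.** They rest on an assumed share that has no source in the documents.

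**Conclusion.** The point holds for the definition and reporting of the primary safety endpoint. As written in section 4.0, the endpoint cannot count a local reaction that impairs the limb for 24 hours or more, and no other section repairs this. That conclusion follows from the wording alone and needs no numerical assumption.

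The likely size is uncertain. At the protocol's own lower bound for limited arm movement, at least about 20 of 200 or 27 of 275 participants would have some limitation. How many would fall outside both levels depends wholly on the unstated share lasting 24 hours or more. The illustrative ranges also assume that a rate listed for adults in general applies to all five groups, including transplant recipients.

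The events themselves should still reach the adverse event record, and no sample size, power figure or stated decision changes. The correction is worth making because the gap lies at the worst end of a named primary endpoint and is cheap to close.

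**What to change.** In section 4.0, replace the two levels with an exhaustive, ordered set:

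1. no local reaction;
2. local reaction without impairment;
3. impaired use of the extremity for less than 24 hours;
4. impaired use of the extremity for 24 hours or more.

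State where impaired activity that does not involve the extremity is counted. Add the duration of impairment to the adverse event form. In section 13.0, say how the severity record corresponds to these levels. Report the number of participants at every level, by group.

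The cost is one line in section 4.0 and one form field, with a short cross-reference in section 13.0. Side effects are already collected at follow-up visits, so no visit is added. The change should be in place before data are collected, because those visits fall days after vaccination and a duration that was not asked about may not be recoverable later.
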